8.4.2.7 Screening for drug abuse

Urine samples will be collected for a testing for Amphetamines/MDMA Screen, Antidepressants Screen, Barbiturates Screen, Benzodiazepines Screen, Cannabinoids Screen, Cocaine Screen, Opiates Screen, Methadone Screen, Propoxyphene, Phencyclidine (PCP), as per the assessment schedule Table 8-1. Participants will be excluded by exclusion criterion 30 if the treating physician determines the presence of ongoing drug abuse. Participants testing positive (e.g. for prescription medications) are not automatically excluded.

8.4.3 **Pregnancy and assessments of fertility**

Pregnancy

All pre-menopausal women who are not surgically sterile will have pregnancy testing. Additional pregnancy testing might be performed if requested by local requirements.

Women of child-bearing potential (WOCBP) are defined as all females physiologically capable of becoming pregnant.

A serum β -hCG test will be performed at the Screening and Baseline Visits for all WOCBP. A positive test at either visit is an exclusion criterion for participating in the study.

From baseline onwards the urine pregnancy dipstick test will be repeated every four weeks up to and including the follow up visit (see Table 8-1) including at weeks 28, 36, and 44, when there are no scheduled site visits. The tests will be performed at the clinical center or at participant's home. In case of home pregnancy test, the women of child-bearing potential will be provided with urine pregnancy test kits. The result will be documented in the participant diary and must be provided to the investigator at next scheduled visit. In case of positive urine pregnancy dipstick test the participant must contact investigator immediately. A positive urine pregnancy test after start of study drug requires its immediate interruption until serum β -hCG is performed and found to be negative. If positive, the participant will enter the post-treatment follow up period. See also Section 10.1.4

Additional pregnancy testing might be performed if requested by local requirements.

After Baseline a serum β -hCG test will be performed when there is positive urine pregnancy dipstick test.

Female participants of child-bearing potential, who are or might become sexually active, must be informed of the need to prevent pregnancy during the study and for 5 days after study completion.

The decision on the contraceptive method should be reviewed at least every 3 months to evaluate the individual need and compatibility of the method chosen and the need for additional pregnancy testing.

Assessments of fertility

Medical documentation of oophorectomy, hysterectomy, or tubal ligation must be retained as source documents. Subsequent hormone level assessment to confirm the woman is not of child-bearing potential must also be available as source documentation in the following cases:

Surgical bilateral oophorectomy without a hysterectomy

Reported 12 months of natural (spontaneous) amenorrhea with an appropriate clinical profile.

In the absence of the above medical documentation, FSH testing is required of any female participant regardless of reported reproductive/menopausal status at screening/baseline.

8.4.4 Other safety evaluations

8.4.4.1 Electrocardiogram (ECG)

ECGs must be recorded after 10 minutes rest in the supine position to ensure a stable baseline. The preferred sequence of cardiovascular data collection during study visits is ECG collection first, followed by vital signs, and blood sampling. The Fridericia QT correction formula (QTcF) should be used for clinical decisions. Single 12 lead ECGs are collected. The original ECGs on non-heat sensitive paper, appropriately signed, must be collected and archived at the study site.

A standard 12-lead ECG will be recorded at the visits indicated in Table 8-1. Determination of eligibility will be based on the ECG report from the central ECG review, not on the ECG machine-generated report.

All ECGs must be performed on the ECG machines provided by vendor assigned for the study by Novartis.

All ECGs will be independently reviewed. Instructions for the collection and transmission of the ECGs to the independent reviewer will be provided in the ECG investigator manual.

12-lead ECG parameters (RR, HR, PR, QRS, and QT) are to be assessed. Each ECG tracing should be labeled with the study number, participant initials, participant number, date and time, and kept in the source documents at the study site. Additional, unscheduled, safety ECGs may be repeated at the discretion of the investigator at any time during the study as clinically indicated. For any ECGs with participant safety concerns, two additional ECGs must be performed to confirm the safety finding. Clinically significant ECG findings at baseline must be discussed with the Novartis before administration of study treatment. Clinically significant abnormalities must be recorded on the relevant section of the medical history/Current medical conditions/AE eCRF page as appropriate.

Local ECG collection may be used during a public health emergency as declared by Local or Regional authorities, i.e, pandemic, epidemic or natural disaster that limits or prevents on-site study visits.

[figure not shown]
If participants cannot visit the site for protocol specified safety ECG assessments, an alternative local facility, collection site or relevant clinical facility that are certified for ECG collection may be used.

8.4.5 Appropriateness of safety measurements

[figure not shown]
The safety assessments selected are standard for this indication/participant population and have been used in previous trials in this indication or deemed appropriate based on non-clinical and early clinical experience. Participants are seen frequently during treatment and will be assessed for safety parameters, including AE of special interest for the study medications.

	I	
		•

Novartis	Confidential	Page 114 of 160
Amended Protocol Version 02 (Clean)		Protocol No. CLJN452D12201C

Novartis Amended Protocol Version 02 (Clean)	Confidential	Page 116 of 160 Protocol No. CLJN452D12201C

9 Discontinuation and completion

9.1 Discontinuation from study treatment and from study

9.1.1 Discontinuation from study treatment

Discontinuation of study treatment for a participant occurs when study treatment is permanently stopped for any reason (prior to the planned completion of study drug administration) and can be decided by either the participant or the investigator.

The investigator must discontinue study treatment for a given participant if, he/she believes that continuation would negatively impact the participant's well-being.

Discontinuation from study treatment is required under the following circumstances:

- participant/guardian decision
- Pregnancy (see Section 8.4.3 and Section 10.1.4)
- Any situation in which continued study participation might result in a safety risk to the participant (including life-threatening events considered to be related to study medication)
- Following emergency unblinding
- Emergence of the following adverse events:

- For ALT, AST, TBL and/or alkaline phosphatase elevations mandating study treatment discontinuations (see Sections 10.2.1 and Section 16.2 for further instructions and monitoring).
- Any evidence of liver decompensation as defined by ascites, bleeding esophageal varices, hepatic encephalopathy, jaundice.
- Serious COVID-19 infection requiring hospitalization

If the decision of discontinuing the study medication comes from the participant, the investigator should make a reasonable effort to understand the primary reason for the participant's discontinuation from study treatment and record this information.

Participants who discontinue from study treatment agree to return for the end of treatment and follow up visits indicated in the assessment schedule (Table 8-1).

If the participant cannot or is unwilling to attend any visit(s), the site staff should maintain regular telephone contact with the participant, or with a person pre-designated by the participant. This telephone contact should preferably be done according to the study visit schedule.

After discontinuation from study treatment, at a minimum, the following data should be collected at clinic abbreviated visits or via telephone/email contact:

- New / concomitant treatments
- Adverse Events / Serious Adverse Events

The investigator must also contact the IRT to register the participant's discontinuation from study treatment.

If discontinuation occurs because treatment code has been broken, please refer to Emergency breaking of treatment code see Section 6.6.2.

9.1.2 Discontinuation from study

Discontinuation from study is when the participant permanently stops receiving the study treatment, and further protocol-required assessments or follow-up, for any reason.

If the participant agrees, a final evaluation at the time of the participant's study discontinuation should be made as detailed in the assessment table (refer to Section 8).

9.1.3 Lost to follow up

For participants whose status is unclear because they fail to appear for study visits without stating an intention to discontinue from study treatment or discontinue from study or withdraw consent/oppose to the use of their data/biological samples, the investigator must show "due diligence" by documenting in the source documents steps taken to contact the participant, e.g. dates of telephone calls, registered letters, etc. A participant should not be considered as lost to follow-up until due diligence has been completed or until the end of the study.

Novartis

9.2 Withdrawal of informed consent/Opposition to use data/biological samples

Participants may voluntarily withdraw consent to participate in the study for any reason at any time. Withdrawal of consent/opposition to use data/biological samples occurs only when a participant:

- Explicitly requests to stop use of their biological samples and/or data (opposition to use participant's data and biological samples)
- No longer wishes to receive study treatment
- Does not want to participate in the study anymore, and
- Does not want any further visits or assessments, and
- Does not want any further study related contacts

This request should be in writing (depending on local regulations) and recorded in the source documentation.

In this situation, the investigator should make a reasonable effort (e.g. telephone, e-mail, letter) to understand the primary reason for the participant's decision to withdraw his/her consent/opposition to use data/biological samples and record this information.

Where consent to the use of Personal and Coded Data is not required in a certain country's legal framework, the participant therefore cannot withdraw consent. However, they still retain the right to object to the further collection or use of their Personal Data.

Study treatment must be discontinued and no further assessments conducted, and the data that would have been collected at subsequent visits will be considered missing.

Further attempts to contact the participant are not allowed unless safety findings require communicating or follow-up.

If the participant agrees, all efforts should be made to complete a final evaluation at the time of the participant's withdrawal of consent/opposition to use data/biological samples should be made as detailed in the assessment table.

Novartis will continue to retain and use all research results (data) that have already been collected for the study evaluation, including processing of biological samples that has already started at time of consent withdrawal/opposition. No new Personal Data (including biological samples) will be collected following withdrawal of consent/opposition.

9.3 Study completion and post-study treatment

Study completion is defined as when the last participant finishes their Study Completion visit and any repeat assessments associated with this visit have been documented and followed-up appropriately by the Investigator or, in the event of an early study termination decision, the date of that decision.

A participant will be considered to have completed the study when the participant has completed the last visit planned in the protocol.

Continuing care should be provided by investigator and/or referring physician based on participant availability for follow-up.

The investigator must provide follow-up medical care for all participants who are prematurely withdrawn from the study, or must refer them for appropriate ongoing care.

For all participants who discontinue treatment early or who complete treatment, a safety followup visit (EOS, Week 52) should be conducted 4 weeks after last treatment (EOT, Week 48). The information to be collected at this follow up visit includes concomitant medications, adverse events, and laboratory samples, as detailed on Table 8-1.

All SAEs reported during this time period must be reported as described in Section 10.1.3.

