If the answer to the primary question is yes, additional questions may be assessed:

Does the monotherapy (tropifexor OR licogliflozin) alone, taken once per day by participants with NASH and stage 2 or 3 fibrosis over 48 weeks, result in histologic improvement compared with placebo?

If the answer to this question is yes as well, then another question will be evaluated:

Does the combination therapy lead to more histological improvement than monotherapies?

For each primary estimand, the population, endpoint, and summary measure for the additional questions are the same as those for the primary question. Only the treatment will change accordingly. For the first additional question, the treatment of interest would be monotherapy and the control would be placebo, whereas for the second additional question, the treatment of interest would be combination therapy and the control would be monotherapy.

Intercurrent events of primary estimand will be addressed with various strategies (considering that these events occur before the histological assessments at Week 48):

- 1. Bariatric surgery: participants who have undergone bariatric surgeries during trial participation are considered as non-responders (composite variable strategy).
- 2. Use of alcohol above protocol permitted amount: the intercurrent events (overuse of alcohol) will be ignored for estimation (treatment policy strategy).
- 3. Addition or removal of any medication that may have a confounding effect on the endpoints: the treatment effect will be assessed with the intercurrent event ignored (treatment policy strategy); in the supplementary analysis, the treatment effect will be imputed as if the intercurrent event doesn't occur (hypothetical strategy)
- 4. Premature discontinuation of study treatment due to tolerability, efficacy, adherence, or adverse event: participants who discontinue the treatment after Week 24 will be asked to have their biopsies assessed at Week 48 regardless of the intercurrent event (treatment policy strategy), participants who discontinue the treatment before Week 24 will be considered as non-responders (composite variable strategy), and participants who have no biopsy extracted at Week 48 will be considered as non-responders (composite variable strategy).
- 5. Death, transplantation and other clinical outcomes: participants will be considered as non-responder (composite endpoint strategy).

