6.1.4 Treatment duration

The planned duration of treatment is 48 weeks. Participants may be discontinued from treatment earlier due to unacceptable tolerability, disease progression and/or at the discretion of the investigator or the participant.

Novartis	Confidential	Page 78 of 160
Amended Protocol Version 02 (Clean)		Protocol No. CLJN452D12201C
If discontinuation of study treatment	occurs, the participant	should NOT be considered
withdrawn from the study. The participation	ant should return to the c	clinic as soon as possible, after
discontinuation of study drug. In this	case, if the participant	and study investigator agree,
participant may continue in the study w	vithout treatment.	
	Alternatively, a study	treatment discontinuation visit

will be conducted.

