Participants should be seen for all visits/assessments as outlined in the assessment schedule (Table 8-1) or as close to the designated day/time as possible. Missed or rescheduled visits should not lead to automatic discontinuation. The date of each scheduled visit is calculated with the appropriate interval from the date of the Baseline/randomization visit, not from the date of the previous visit. If a scheduled visit is late by more than half of the planned interval between it and the next scheduled visit, the visit should be skipped.

If the COVID-19 or any other pandemic limits or prevents on-site study visits, alternative methods of providing continuing care may be implemented. Phone calls, virtual contacts (e.g. teleconsulting) or visits by site staff/home nursing service at the participants home depending on local regulations and capabilities, may be considered. In-home visits would be conducted by the site staff (under the responsibility of the investigator), or by a health care provider (HCP) supporting this activity if this is in agreement with the investigator.

Participants who discontinue from study treatment for any reason (see Section 9.1 for more details) should be scheduled for an end of treatment visit as soon as possible, and attend the follow-up visits as indicated in the Assessment Schedule.

Novartis	
Amended Protocol Version 02 (Clean)

Confidential

Participants who discontinue from study or withdraw their consent/oppose the use of their data/biological samples should be scheduled for a final evaluation visit if they agree, as soon as possible, at which time all of the assessments listed for the final visit will be performed. At this final visit, all dispensed investigational product should be reconciled, and any adverse event and concomitant medications not previously reported must be recorded on the electronic case report form (eCRF).

The "X" in the table denotes the assessments to be recorded in the clinical database or received electronically from a vendor. The "S" in the table denotes the assessments that are only in the participant's source documentation and do not need to be recorded in the clinical database.

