¹¹ Women Of Child Bearing potential (WOCBP) must have a urine dipstick pregnancy test every 4 weeks, including at week 28, 36 and 44 (when there are no study visits), up to and including the follow up visit.

¹² After Baseline visit onwards serum sample to be collected for serum pregnancy test only if urine dipstick test is positive – During the study if test is positive, the participant must be discontinued from study drug.

¹⁷ At Baseline and week 4, to be collected at least 1-2 hours post dose at clinic.

¹⁸ Update as necessary

¹⁹ Update as necessary - SAEs must be reported & recorded until 30 days after the participant has stopped study participation; see appropriate protocol Section 10.1.2.

²¹ For participants who discontinue study treatment prematurely before the end of the treatment period for any reason other than withdrawal of informed consent, the Week 48, End of Treatment (EOT) and Week 52 End of Study (EOS) visits must be performed.

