12.4.4 Handling of missing values not related to intercurrent events

While not possible to confirm missing completely at random (MCAR), the histological response status from the early termination visit after at least 24 weeks of study treatment will be used for the primary analysis in case of missing primary endpoint at week 48. Participants otherwise with primary endpoint missing or any primary endpoint after intercurrent events will have the values imputed using multiple imputation (MI) methods (Rubin 1976, Rubin 1987) under a missing at random (MAR) assumption.

For multiple imputation: an arbitrary missing pattern will be assumed and a fully conditional specification (FCS) method with logistic regression will be applied. The logistic model will be used to analyze the multiple imputed datasets, and pooled results will be obtained based on Rubin's combination rules. More implementation details of the multiple imputation (MI) will be specified in the SAP.

The proportion of participants with missing primary endpoints at week 48 will be compared among the combination therapy, monotherapies and the placebo.

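### For participants who stop treatment after Week 24, the visit rules disagree on when the follow-up biopsy falls due, and an early biopsy with none at Week 48 has three incompatible classifications

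*Protocol*

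**What the plan says.** **Timing.**
- Protocol 2.1, intercurrent event 4, repeated in 12.4 and 12.4.3: "participants who discontinue the treatment after Week 24 will be asked to have their biopsies assessed at Week 48 regardless of the intercurrent event". This is labelled treatment policy.
- Protocol 8: anyone who stops study treatment "should be scheduled for an end of treatment visit as soon as possible, and attend the follow-up visits as indicated in the Assessment Schedule". The same section counts visit dates from randomisation.
- Protocol 9.3, for early discontinuers and completers alike: the safety visit, labelled EOS and Week 52, "should be conducted 4 weeks after last treatment (EOT, Week 48".
- Table 8-1 footnote 21, for premature discontinuation other than by withdrawal of consent: "the Week 48, End of Treatment (EOT) and Week 52 End of Study (EOS) visits must be performed". It does not say whether these are calendar weeks or visits brought forward.
- Table 8-1 footnote 5d makes the Week 48 biopsy optional only for stops before 24 weeks.
- Protocol 6.1.4: stopping treatment is not withdrawal, and, if both sides agree, the "participant may continue in the study" off treatment. The alternative is a treatment discontinuation visit.

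**Classification.**
- 2.1, 12.4 and 12.4.3 count a participant with no Week 48 biopsy as a non-responder.
- 12.4.4, first sentence: when the Week 48 endpoint is missing, "the histological response status from the early termination visit after at least 24 weeks of study treatment will be used for the primary analysis".
- 12.4.4, second sentence: other missing endpoints, and any endpoint after an intercurrent event, are multiply imputed.

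The SAP (December 2019) uses the last histology after at least 24 weeks of treatment (2.5). It assigns any biopsy from study day 170 to end of study to Week 48 (Table 2-1, Group 5).

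**The concern.** The primary estimand compares arms at Week 48 whether or not treatment was stopped. A biopsy taken soon after a stop at Week 26 answers a different question: the effect of about half the planned exposure, with little or no time off drug. Table 8-1 as supplied has no separate treatment-discontinuation column, and its only post-baseline biopsy sits in the Week 48 column, which footnote 21 calls EOT. A site that brings EOT forward may therefore take the biopsy then. Section 4.5.3 describes one pair of biopsies, at screening and Week 48.

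If the biopsy is taken early and not repeated, responder status on both primary endpoints depends on which protocol section the analyst follows. Leaving that choice open until the data are seen is what pre-specification is meant to prevent. A biopsy taken at the wrong time cannot be repaired later.

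**Working it through.** **1. Timing, for a stop at Week 26.**
- Section 8 read literally: EOT at about Week 26.
- 9.3 read literally: EOS at 26 + 4 = Week 30, which is 18 weeks before the biopsy that 2.1 asks for. On this reading, visits end before Week 48 for any stop before Week 48 - 4 = 44.
- Footnote 21 read by calendar, with 6.1.4: the participant stays in the study and has the Week 48 and Week 52 visits.

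The protocol does not say which reading governs.

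**2. Classification, given an early biopsy and none at Week 48.**

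| Source | Outcome |
|---|---|
| 2.1, 12.4, 12.4.3 | Non-responder |
| 12.4.4, first sentence | Early histology |
| 12.4.4, second sentence | Multiply imputed |

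The heading of 12.4.4 limits it to missing values unrelated to intercurrent events. That does not separate the cases, because 12.4 lists any early treatment discontinuation before the Week 48 visit as an intercurrent event.

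**3. SAP window.** Day 337 (target) - day 170 (start of window) = 167 days, about 24 weeks.

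**4. Reproducing the stated power.** Inputs from Protocol 12.4.2 and 12.8.1: combination 140, placebo 80; endpoint A 35% vs 20%; endpoint B 25% vs 10%; participant-level correlation 0.5; two-sided alpha 0.05 / 2 = 0.025 per endpoint; z-test without continuity correction; success on at least one endpoint. Simulation with 400,000 runs and unpooled variance, z = (p1 - p2) / sqrt(p1(1 - p1)/n1 + p2(1 - p2)/n2), gives 0.850 against 0.85 in Table 12-5. The 95/95 allocation gives 0.801 against 0.80. Pooled variance gives 0.801 at 140/80, so the unpooled form is used below.

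**5. Effect of the classification.** Let f be the share of an arm with an early biopsy and none at Week 48. The documents do not give f. They expect around 20% missing Week 48 biopsies for all reasons (0.20 x 380 = 76), so 20% is taken as the top of the range. If early histology is used and responds at the planning rates, power stays at 0.85. If these participants are non-responders, each rate is multiplied by (1 - f). The 15-point difference on each endpoint becomes 15 x (1 - f), with the correlation held at 0.5.

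| f, both arms | Difference, each endpoint | Power |
|---|---|---|
| 0 | 15.0 points | 0.85 |
| 5% | 14.25 | 0.83 |
| 10% | 13.5 | 0.80 |
| 15% | 12.75 | 0.77 |
| 20% | 12.0 | 0.74 |

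If only the combination arm were affected, power would be 0.78, 0.70 and 0.51 at f = 5%, 10% and 20%. This is a bounding case, not a forecast. The multiple-imputation outcome was not simulated.

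**The case against.** The strongest reply is that the protocol already requires Week 48 follow-up. Footnote 21 says these visits must take place, Section 8 counts visits from randomisation, footnote 5d makes the biopsy optional only for stops before 24 weeks, and 6.1.4 says stopping treatment is not withdrawal. Section 9.1.1 prefers telephone contact on the visit schedule when visits are not attended. The 9.3 sentence concerns a safety visit and itself carries the Week 48 and Week 52 labels. Section 8.3.1.8, to which Table 8-1 refers for biopsy details, is not in the text supplied, and 6.1.4 has a gap where procedures after a stop might be described.

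This stands to the following extent. A reader might infer that the visit rules end the study early and displace the Week 48 biopsy. The documents do not support that: they show conflicting rules, not a rule that removes the biopsy.

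On classification, the double reading needs an early biopsy and no Week 48 biopsy. SAP Table 2-2 would choose a true Week 48 biopsy over an early one, because it is closer to the target day. SAP 2.5 plans an early-termination assessment for withdrawal from the study, not merely from treatment. Item 4 of 2.1 names particular reasons for stopping, so 12.4.4 could be confined to others. Its second sentence could also be read as covering only those without usable early histology. These readings narrow the problem but do not remove it. The list in 12.4 covers every early stop, and the clause in 12.4.4 on endpoints after intercurrent events is not limited to participants without early histology. The SAP was written for the three-arm, 210-patient design and names while-on-treatment and hypothetical strategies, so it cannot settle a question about the current protocol.

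On size, no document gives the share affected or how it differs by arm. More pruritus is reported with tropifexor than with placebo (4.2), though mostly Grade 1 (1.1.3). At licogliflozin 30 mg, diarrhea was similar to placebo (1.1.4). Unequal stopping is possible but not established. Early biopsies may also respond below the 48-week planning rates, so the power contrast is only an illustration.

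**Conclusion.** The concern holds in two parts. First, for stops after Week 24, Sections 8 and 9.3 conflict with footnote 21, 6.1.4 and the Week 48 estimand, and sites could follow either reading. Second, when an early biopsy exists and a Week 48 biopsy does not, the current protocol gives three incompatible outcomes for both primary endpoints. The second part rests on protocol text alone and does not depend on the outdated SAP.

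The size is conditional. With 5-20% of both arms affected (an assumption) and early histology responding at the planning rates, the choice between the first two outcomes is worth 0.85 against about 0.83-0.74 in power. At an equal 5% the loss is small. The case for correction is that responder status on the primary endpoints must not be open to choice, whatever the share turns out to be.

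**What to change.** 1. Reconcile Section 8, 6.1.4, 9.3 and Table 8-1 footnotes 5d and 21 with the Week 48 estimand. Separate the treatment-discontinuation visit from the Week 48 visit, and state that the latter is counted from randomisation for those who remain in the study.
2. State one classification for an early biopsy without a Week 48 biopsy, in the same words in 2.1, 12.4, 12.4.3 and 12.4.4, and delete the sentences that conflict with it. Settle this before unblinding.
3. When the SAP is updated to the four-arm design, align its intercurrent-event strategy (2.5) and its Group 5 biopsy window (day 170 to end of study) with that rule.

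The cost is protocol and SAP wording; no planned biopsy is added. One small downside is that some participants off treatment may decline the later biopsy, and the chosen rule must then cover them.
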